Beacon Sensors & Telerehabilitation to Assess & Improve use of Devices for visual functioning (BeST-AID)

NCT04066075

Protocol date: April 1, 2020

Beacon Sensors & Telerehabilitation to Assess & Improve use of Devices for visual functioning (BeST-AID)

Specific Aims: Indicate the purpose of the research, specifying the problems and/or hypotheses to be addressed.

Difficulty with reading is the chief complaint of most patients who present for low vision rehabilitation (LVR). Devices that provide magnification (i.e., hand-held or stand optical magnifiers, electronic magnifiers, or spectacle-based magnification as high adds) are commonly prescribed for this indication; however, about one in five patients will abandon their magnifier within three months. The successful application of magnification devices is predicated on their correct use while reading, which can require additional training sessions following the initial dispense of the device to further improve visual functioning. Many patients with low vision (LV) are unable to attend multiple training sessions in-office due to barriers related to transportation and/or co-morbidities. A promising solution to this problem is real-time videoconferencing to provide telerehabilitation, which involves remotely delivered LVR services by a LVR provider in-office to a patient at home. However, there are currently no publications on whether telerehabilitation can improve LV patient outcomes. We recently completed a small pilot study in which we showed that telerehabilitation for LV was feasible and acceptable by both patients and LVR providers. We next propose to further explore and develop our telerehabilitation protocol targeted at improving visual function outcomes in LV patients, so it can be evaluated in a phase III clinical trial in the future.

Specific Aims:

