To assess the potential for telerehabilitation to enhance visual function by providing remotely-delivered LVR training to use magnification devices (i.e., hand-held or stand optical magnifiers, electronic magnifiers). Following basic LVR (i.e., one in-office training session) for new magnification device(s), we aim to determine if there is additional gain in visual functioning by randomizing subjects (2:1) to telerehabilitation or additional in-office LVR (active control). This will help provide estimates of effect size to plan a future larger-scale randomized controlled trial. We will compare visual function changes with the Activity Inventory questionnaire and validated reading tests in 60 LV patients with central vision loss due to any ocular disease recruited from 10 centers. Participants will be assessed before and after two consecutive periods: (1) no further training will be provided for one month after a single LVR training session (i.e., basic LVR), followed by (2) up to three LVR sessions over a three month period either via telerehabilitation (n=40) in the participants' homes with study loaner equipment (iPad/smartphone, stand, reading cards) via remote control assistance, or in-office LVR (active control; n=20). Multiple sessions will be conducted if the LVR provider deems the participant is not completely proficient with their magnification device. We will determine which patient characteristics and/or magnification devices are most likely to benefit from telerehabilitation, to be targeted in a future, larger-scale, phase III trial.

The primary goal of this proposal is to refine the methods and procedures for implementing these innovative technologies for LVR, in order to develop future protocols for randomized controlled trials. In the future, we envision that telerehabilitation could improve efficiency and patient outcomes by changing the method by which follow-up LVR services are provided. This is a high priority given the increasing prevalence of LV, paucity of LVR providers, and barriers related to transportation and geography.

Background and Significance: Provide a summary of the background for this study and explain how it will contribute to existing knowledge.

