A clinical model for LV telerehabilitation has already been implemented, in which the patient attends a video session at their local optometrist's office (not their home) with remotely located LVR providers at the Buffalo VA in NY. It is important to conduct research to document changes in patient outcomes following telerehabilitation, to provide evidence-based practice recommendations for this modality and future insurance reimbursement. Our eventual goal is to conduct a randomized controlled trial of telerehabilitation for LV compared to active in-office LVR (possibly an equivalence trial) to improve patients' visual function and reduce magnifier device abandonment. Given the projected dramatic increase in the expected number of people with LV over the next several decades, it is imperative to validate creative solutions to provide LVR to overcome economic and societal burdens caused by LV, and increase access to and quality of care for these individuals.

Premise:

There is a need for a clinical trial of telerehabilitation since the literature and a Cochrane systematic review completed by the PI and co-I, [name], revealed that telerehabilitation has rarely been applied to LV and there are no published outcomes from studies (i.e., no evidence of efficacy). The rationale for telerehabilitation is supported by previous studies indicating that transportation, geography, patients' co-morbidities and the paucity of providers are barriers to receiving LVR in-office. It is premature to propose a large-scale, phase III randomized controlled trial (RCT) at this time since the following are yet unknown: effect size (i.e., possibility of visual function enhancement), which patients and/or magnification devices are most likely to benefit, appropriate number of telerehabilitation sessions for proficiency, and feasibility of in-office LVR as an active control; the current study will assess these factors and then design an RCT based on findings.

Innovation:

There are several innovative elements in the proposed research program:

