will follow a standard protocol for the schedule of visits and number of sessions, but the intervention itself is considered standard of care. We considered using 'usual care' as a control but decided against it since there is no standard for the number of sessions and content delivered during the training, as much variability exists for the LVR practices of our providers; some do not tend to conduct multiple training sessions when new magnification devices are prescribed, while others will have one or more additional LVR session(s). Usual care comparator trials are also vulnerable to the Hawthorne effect in which practice may be influenced by the fact that providers are being studied. We are proposing the same standardized schedule of visits for both telerehabilitation and active controls in-office to keep the dosing of the interventions consistent in this parallel design trial. We anticipate that usual care will involve fewer LVR sessions and thus result in worse outcomes than a strict active control intervention, thus there is limited value to study usual care at this stage. Adding a third arm for usual care in the proposed trial would significantly increase the required sample size, which would be outside of the scope of this project. In the future, a much larger scale effectiveness trial can be designed to compare telerehabilitation to usual care practices.

Subjects and Magnification Devices:

Subject identification and recruitment will occur at all study sites. Adult participants will be recruited from the patients seen in the LVR service at four academic centers: (1) New England College of Optometry (NECO) in Boston, MA, (2) University of Nebraska Medical Center (UNMC) in Omaha, NE, (3) Southern California College of Optometry (SCCO) in Fullerton, CA and (4) University of California, Los Angeles (UCLA) and six private practices (Mid-Michigan Eye Care; Low Vision Services, PLC; See What You Miss Optometry; Frank Stein & Paul S. May Center for Low Vision Rehabilitation; Boston University Eye Associates, Inc.; Family Eyecare of Orange & Solinsky Eyecare LLC). Eligible patients will have newly received following types of magnification devices (multiple devices allowed): hand-held optical magnifiers, portable electronic video magnifiers, some stand magnifiers and CCTVs. Study screening, consent and enrollment procedures will only take place at UCLA and will only be conducted by the study team members at UCLA, which will include oral consent by phone.

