Per study visit/session to receive telerehabilitation or training in-office = approx. one hour

Per study telerehabilitation session to complete follow-up survey = approx. 15-30 minutes

Per study session to complete questionnaire outcome measures by phone = approx. 2-3 hours

Total anticipated time commitment per subject = approx. 8-15 hours over 4 months

Statistics and Data Analysis: Describe the proposed statistical procedures or descriptive analyses for the study. If applicable, indicate how the sample size was determined.

Data analyses: Data management will be an ongoing task for the PI.

Descriptive statistics will be used to summarize the study data and findings. We will determine the effect sizes for basic LVR (one session in-office as part of standard of care), additional in-office LVR (active control), and telerehabilitation for changes in the Activity Inventory and reading outcomes by comparing the scores at each follow-up to baseline (pre-LVR). For the Activity Inventory questionnaire, we anticipate that the reading domain may have the largest magnitude of change since magnification devices are most often used for reading tasks, which is the chief complaint of most LV

patients. For the MNread test, we will primarily focus our analyses on reading acuity and maximum reading speed. Separate analyses (sub-groups) for all outcomes will be used to compare outcomes for participants with hand-held or stand-based magnifiers (optical or electronic) versus spectacle-based high add power magnification (hands-free).

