Multiple regression analyses will assess if effect sizes for the telerehabilitation and in-office LVR control group (i.e., changes in the outcomes: Activity Inventory score, reading speed) are related to the number of telerehabilitation sessions, patient demographics, visual acuity, contrast sensitivity, diagnosis, or scores on the SF36, Telephone Interview for Cognitive Status (TICS), Geriatric Depression Scale, or Hospital Anxiety Depression Scale questionnaires. We will apply advanced statistical methods (e.g., multilevel models) for missing data. We will perform a Rasch analysis of our Activity Inventory data in comparison to a very large database of LV patients (several thousand) who have completed the Activity Inventory. Goals and activities have their item measures, and the fit properties of the Activity Inventory from the database of previous responses can be used to convert raw scores into person measures. In the event of non-normally distributed data, we will use a binary outcome (proportion of subjects with improvement greater than 0.14 logits) to compare changes between telerehabilitation and in-office LVR for the Activity Inventory domains using chi-square tests and logistic regressions.

Sample Size calculation: We plan to enroll and compare findings for two equal sized groups based on visual acuity (VA); i.e., those better or worse than 20/63. A sample size calculation for matched pairs t-test revealed that 18 subjects in each of the 2 groups would detect a within-subject mean improvement of 0.14 logits on the Activity Inventory (primary outcome) following telerehabilitation (equivalent to 1-line or 0.1 logMAR VA), when considering a standard deviation of 0.17 logits for the differences, power of 0.80 and 0.05 type I error probability. We will aim to enroll a total of ~40 subjects randomized to telerehabilitation (given our 2:1 randomization plan), and aim to have a total of ~20 active controls randomized to receive in-office LVR. We will determine the effect sizes for basic LVR (one session in-office as part of standard of care), telerehabilitation and additional in-office LVR for changes in the Activity Inventory and reading outcomes.

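### The only planned device comparison uses spectacle high adds, which the plan's own device lists omit; secondarily, the session-count regression is not set up to inform how many sessions are needed

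*Combined protocol and SAP*

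**What the plan says.** **Devices.** The opening of the protocol counts high adds among commonly prescribed magnification devices ("or spectacle-based magnification as high adds"). The aim itself is narrower. It concerns training to use "magnification devices (i.e., hand-held or stand optical magnifiers, electronic magnifiers"), with no high adds. Subjects and Magnification Devices requires newly received "types of magnification devices (multiple devices allowed): hand-held optical magnifiers, portable electronic video magnifiers, some stand magnifiers and CCTVs", again without high adds. The Data analyses text then plans subgroup analyses, for all outcomes, of "hand-held or stand-based magnifiers (optical or electronic) versus spectacle-based high add power magnification (hands-free"). Device type is not among the regressors listed later in that section.

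**Sessions.** The Specific Aims allow "up to three LVR sessions over a three month period either via telerehabilitation" or in-office, with multiple sessions if the provider judges that the participant is not fully proficient. Research Plan and Methods describes a standard protocol for visits and number of sessions, common to both arms. The text introducing the outcomes accepts that adherence to scheduled sessions may differ between arms. The regression asks whether changes in outcome "are related to the number of telerehabilitation sessions, patient demographics, visual acuity, contrast sensitivity, diagnosis" and several questionnaire scores.

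**Purpose.** The Specific Aims state: "We will determine which patient characteristics and/or magnification devices are most likely to benefit from telerehabilitation". The Premise lists among the unknowns this study will assess: "which patients and/or magnification devices are most likely to benefit, appropriate number of telerehabilitation sessions for proficiency".

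**The concern.** Two of the reasons given for running this study before a larger trial are to learn which devices benefit and how many sessions proficiency takes. The analysis text does not match either question well.

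The device analysis compares a class that is enrolled with one that the eligible list does not admit. It leaves uncompared the classes that will be enrolled, such as optical and electronic magnifiers. If nothing changes, the study may end with no usable device result for targeting the next trial.

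The session analysis is a lesser matter. A slope of outcome change on sessions delivered could be read at the planning stage as the value of an extra session. The way the count arises does not support that reading. The quantity that the Premise asks about, sessions to proficiency, has no named summary.

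**Working it through.** **1. Can both sides of the device comparison be filled?**

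| Place | High adds included? |
|---|---|
| Opening background paragraph | Yes, as commonly prescribed devices; not an eligibility rule |
| Aim's device definition | No |
| Eligible list, Subjects and Magnification Devices | No |
| Subgroup comparison, Data analyses | Yes, as one whole side |

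A participant whose only device is a high add does not meet the eligible list. Because more than one device is allowed, a participant may hold a high add as well as an eligible device. That person belongs to both sides, and no rule assigns them to one. So the high-add side has either no members or only overlapping members.

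**2. What could a comparison of enrolled classes deliver?** The plan gives no size, power or precision for any device comparison, so there is no figure to reproduce. Inputs from the Sample Size calculation: SD of change 0.17 logits, about 40 telerehabilitation participants and about 20 controls. Assumptions: the 0.17, given there for within-subject differences after telerehabilitation, applies in each device class and arm; the class splits are illustrative; nobody drops out.

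Two classes within one arm: half-width = t(n−2) × 0.17 × √(1/k + 1/(n−k)), n = 40, t(38) = 2.024.
- 20 v 20: 2.024 × 0.17 × √(1/20 + 1/20) = 2.024 × 0.0538 = 0.109
- 30 v 10: 2.024 × 0.17 × √(1/30 + 1/10) = 2.024 × 0.0621 = 0.126

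Device-by-arm comparison, classes split 20/20 in telerehabilitation and 10/10 in controls, t(56) = 2.003:
- 2.003 × 0.17 × √(1/20 + 1/20 + 1/10 + 1/10) = 2.003 × 0.0931 = 0.187

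These figures are for the Activity Inventory only. No SD is given for the reading outcomes.

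**3. What does the session count measure?**
- The count of telerehabilitation sessions is zero for every control. If the arms are pooled, the slope is partly a comparison of arms, and no arm term is listed. If each arm is fitted separately, the count is constant in controls and drops out there.
- If the proficiency rule in the Specific Aims governs, the count follows how the participant was doing. It is then confounded by need, and proficiency is not a listed covariate.
- If the standard protocol means a fixed number, the count varies only through missed visits, and the slope reflects whatever goes with attendance.
- Need and attendance can push the slope in opposite directions. The documents contain nothing from which to size either.

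**4. How well could proficiency by session be described?** Wilson 95% interval: [p + z²/2n ± z√(p(1−p)/n + z²/4n²)] / (1 + z²/n), z = 1.96, with assumed counts.
- 32 of 40 in telerehabilitation: 0.652 to 0.895
- 16 of 20 controls: 0.584 to 0.919

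**The case against.** **The regression claims only a relation.** This is correct. A reader might infer that the slope will be used to choose the number of sessions, but no passage says so. Under the proficiency rule, the tally of sessions delivered already bears on the question in the Premise, and the plan promises descriptive statistics. What remains is narrower: no summary of sessions to proficiency is named, sessions that ended because the participant was proficient are not separated from those missed, and the count is mixed with arm.

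**The bias is not shown.** It is tempting to say that the slope must run low because harder cases get more sessions. The documents do not support a direction or a size. Any figure would rest on outside assumptions, and the sign depends on whether need or attendance drives the count. I give none.

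**The two statements on sessions may not conflict.** They can be read as one common rule applied in both arms. That makes this a request for clarification and not a contradiction.

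**A replacement comparison has limits too.** A contrast inside the telerehabilitation arm cannot separate devices that gain from telerehabilitation from devices that gain under any training. The device-by-arm comparison is needed for that, and it is imprecise. The 0.14 logits in the sample size text is a within-subject improvement and was not set as a standard for device contrasts.

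**High adds might be eligible elsewhere.** One part of the protocol, after the start of the list of procedures at each study site, was not available for this review. A reader might infer that the high-add group is certainly empty; the available text does not go that far. Even if high adds are admitted there, the aim, the eligible list and the analysis would still need to agree.

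**Conclusion.** The device point holds. As written, the plan's one device comparison has a side that is empty or made up only of people who fit both sides, so it cannot tell the sponsor which enrolled devices benefit. This rests on the available text. A comparison of enrolled classes would have a 95% half-width of roughly 0.11 to 0.13 logits within the telerehabilitation arm, and about 0.19 for the device-by-arm comparison, under the SD and splits assumed above.

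The session point holds in a limited form. The regression is not wrong as a stated association, but its regressor is non-randomised, zero in all controls and tied to need or attendance. It does not show what further sessions would add, and the sessions-to-proficiency question is left without a named analysis.

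The change should be made, mainly for the device mismatch. The primary outcome and sample size are unaffected.

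**What to change.** - Reconcile the opening paragraph, the aim, the eligible list and the subgroup text on high adds.
- If the eligible list stands, replace the comparison with one between enrolled classes, for example optical v electronic. Place each participant in one class by a rule fixed in advance, and report the estimate with a 95% CI. Add the device-by-arm comparison if a difference is to be attributed to telerehabilitation, and label it exploratory.
- If high adds are eligible, list them in the aim and the eligible list, and state how participants with both types are classed.
- Fit the session-count association within the telerehabilitation arm only, and label it non-causal.
- For the question in the Premise, report by arm, with 95% CIs, the share judged proficient after each session. Separate sessions that ended on proficiency from sessions missed.
- Reconcile the Specific Aims and Research Plan and Methods on what sets the number of sessions.

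**Cost.** Wording, one field for device class and one for why sessions ended. If the number of sessions is fixed, the second field would not show who was proficient when; a provider rating of proficiency at each existing session would be needed instead. There are no extra visits or participants. If the eligible list stands, this study leaves the high-add question unanswered.

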Sex as a biological variable: We will recruit and enroll both genders, intending to have meaningful representation from both sexes, which should be achievable given our previous experience during our pilot study of telerehabilitation (4 of 10 subjects were men). About two-thirds of LV patients are women, and our survey data indicate women are more interested in our interventions; thus there may be a slightly greater proportion of women in our study. We will examine if gender affects outcomes, along with other potentially influential variables.

Telerehabilitation Methods:

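### The regression meant to show who benefits from telerehabilitation lists at least ten terms for arms of about 40 and 20, states no arm interaction, and is not labelled exploratory

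*Combined protocol and SAP*

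**What the plan says.** Under Data analyses, the combined protocol and SAP states: "Multiple regression analyses will assess if effect sizes for the telerehabilitation and in-office LVR control group" (changes in Activity Inventory score and reading speed) "are related to the number of telerehabilitation sessions, patient demographics, visual acuity, contrast sensitivity, diagnosis, or scores on the SF36", the Telephone Interview for Cognitive Status (TICS), "Geriatric Depression Scale, or Hospital Anxiety Depression Scale questionnaires". Demographics are not listed, but the paragraph on sex as a biological variable adds: "We will examine if gender affects outcomes, along with other potentially influential variables".

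The Sample Size calculation paragraph plans about 40 participants in telerehabilitation and will "aim to have a total of ~20 active controls randomized to receive in-office LVR". The Specific Aims describe "60 LV patients with central vision loss due to any ocular disease recruited from 10 centers", and state the use of the result: "We will determine which patient characteristics and/or magnification devices are most likely to benefit from telerehabilitation", so that these can be targeted in a later phase III trial.

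The text does not say whether the listed items enter one model or whether the arms are pooled. It gives no arm-by-characteristic interaction, variable selection, shrinkage, multiplicity rule or precision target for this analysis, and does not call it hypothesis-generating.

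**The concern.** There are three separate problems.

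- **Too many terms for the sample.** If the listed items go into one model, much of the apparent fit may be chance, and some predictors will look important by accident.
- **The wrong question.** A characteristic that predicts change within an arm, or across pooled arms with a common slope, is prognostic. Identifying who benefits from telerehabilitation rather than in-office LVR requires the association with outcome to differ between arms, which is an arm-by-characteristic interaction.
- **A predictor set after randomisation.** Under the Specific Aims, further sessions are given when the provider judges the participant not yet fully proficient. The coefficient for number of sessions therefore mixes dose with slow progress. In a pooled model, telerehabilitation sessions are also zero for every control, so the variable is largely tied up with arm.

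At stake is the choice of phase III population. The Premise section says the later trial will be designed from these findings.

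**Working it through.** **The plan's own figure.** The only sample-size figure is 18 per visual acuity (VA) group for a paired t-test (difference 0.14, SD 0.17, power 0.80, alpha 0.05). The normal approximation, two-sided, is (0.17 × (1.96 + 0.84) / 0.14)² ≈ 11.6, so 12; the exact t calculation gives 14. With 18, power is about 0.91. The stated 18 therefore exceeds what its inputs require. It says nothing about the regression, for which no size or power is given.

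**Counting terms.** Sessions 1, demographics at least 2 (the word is plural; sex plus at least one other), visual acuity 1, contrast sensitivity 1, diagnosis at least 1, SF-36 at least 1, TICS 1, Geriatric Depression Scale 1, Hospital Anxiety Depression Scale at least 1. That is nine named items and at least 10 terms. In a model for the in-office arm alone, telerehabilitation sessions do not vary, which leaves 9.

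**Fit from noise alone.** If no predictor has any effect, expected R-squared is p/(n−1).

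| Reading | p | n | Participants per term | Residual df | Expected R-squared |
|---|---|---|---|---|---|
| Telerehabilitation arm | 10 | 40 | 4.0 | 29 | 10/39 = 0.26 |
| In-office arm | 9 | 20 | 2.2 | 10 | 9/19 = 0.47 |
| Pooled | 10 | 60 | 6.0 | 49 | 10/59 = 0.17 |

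**Fit when some predictors are real.** The documents give no true R-squared, so it was varied. The simulation assumed 10 terms, pairwise correlation 0.3, three real predictors and 3,000 runs. Cells show mean apparent R-squared, then median out-of-sample R-squared.

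| True R-squared | n=40 | n=60 |
|---|---|---|
| 0.2 | 0.40, −0.08 | 0.33, 0.03 |
| 0.3 | 0.47, 0.05 | 0.41, 0.16 |
| 0.5 | 0.62, 0.32 | 0.58, 0.40 |

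At n=20 (also simulated with 10 terms) the pairs are 0.66, −0.44 at a true value of 0.3, and 0.75, −0.06 at 0.5.

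**Chance predictors.** With no real effects, the chance of at least one p<0.05 among 10 independent tests is 1 − 0.95^10 = 0.40; the simulation gave 0.38 at n=40. Over the two named outcomes, if all 20 tests were independent, it is 1 − 0.95^20 = 0.64.

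**What an interaction could show.** With one standardised characteristic and residual SD 1, the standard error of the slope difference between arms is √(1/40 + 1/20) = 0.274. The difference detectable with 80% power is 2.80 × 0.274 = 0.77 SD per SD. Power for a difference of 0.5 is about 0.45. Even a correctly specified benefit analysis is therefore weak here. Dropout, for which no rate is stated, would make every figure worse.

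**The case against.** The strongest reply is that the plan does not commit to the model being criticised. It speaks of analyses in the plural and joins the items with *or*, and naming both arms fits a pooled model as well as separate ones. This stands. The R-squared figures are conditional on joint entry, and the pooled value is the mildest, at 0.17.

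A reader might infer that the in-office model has ten or more terms and a noise R-squared of 0.53 (10/19). Read literally, the sessions item cannot be a predictor in that arm, so 9 terms and 0.47 is the supportable figure. Higher counts need an assumed coding of diagnosis or subscales.

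A reader might also infer that the answer would be mostly noise. That depends on the unknown true R-squared. In the simulation more than half of the apparent fit is optimism at n=40 and n=60 up to a true value of 0.3. At 0.5 it is about half for n=40 (0.30 of 0.62) and about a third for n=60 (0.18 of 0.58).

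Nor does this regression select devices: device type is not among its predictors and is handled by subgroup analyses in the same section.

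Ordinary regression keeps 5% error per coefficient, so chance findings are a multiplicity problem that fitting one interaction at a time does not remove. Five such interactions in a pooled null simulation (assumed correlation 0.3 among three of the characteristics) gave at least one p<0.05 in 22% of runs. The gain from the fix lies in asking the right question, using all participants and labelling the result honestly.

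Finally, this is a phase 1/2 trial whose primary goal is to refine methods, and the regression is not the basis of its size. That lowers the weight of the point. It does not answer it, because the Specific Aims promise a determination that this analysis cannot give.

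**Conclusion.** The point holds as a low-cost improvement. What does not depend on the choice of model is that no arm-by-characteristic interaction is stated. The analysis as written would describe who changes, while the stated aim concerns who benefits from telerehabilitation. Separate fits per arm could be compared, but the plan states no such comparison. The treatment of number of sessions as a predictor is a further weakness on any reading that includes it.

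The overfitting is conditional: if the items are entered jointly with one column each, noise alone gives R-squared of about 0.26, 0.47 or 0.17 on the three readings. The documents do not support saying that the plan fits one saturated model in each arm, or that the phase III population would necessarily rest on noise. They do support saying that the result can only be hypothesis-generating and that the plan should say so.

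**What to change.** For the question of who benefits:

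- Fit one model on all ~60 randomised participants: month-4 score on month-1 score, arm and VA group. The Activity Inventory and the Sustained Silent Reading test are both scheduled at these times.
- Add one pre-listed baseline characteristic and its arm interaction at a time, from a short list such as age, sex, VA, contrast sensitivity, TICS and one mood score. Use baseline questionnaire values, since these scales are repeated at month 4.
- Report interaction estimates with confidence intervals. Label them hypothesis-generating, because power is low and several are tested.
- In the Specific Aims, change *will determine* to *will explore*.
- Report number of sessions descriptively within arm, not as a predictor of benefit. Keep device type in the planned subgroup analyses.
- If a joint model is wanted, use a shrinkage method and report optimism-corrected R-squared.

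The cost is SAP wording and modest changes to analysis code, with no extra participants, visits or data. There are two losses. Mutually adjusted coefficients for every listed predictor are no longer reported. For this analysis, change is taken from month 1 and not from the pre-LVR baseline that the Data analyses text uses for effect sizes; this separates the randomised period from the response to basic LVR, and should be stated.
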